 - b. Treatment period: tumour assessments will be done every 8 weeks from C1D1 (\pm 7 calendar days) until radiologic progression is documented
 - c. Withdrawal visit: tumour assessments will be performed only if not performed within previous 8 weeks. Every effort should be made to perform the WV tumour assessments prior to the start of new anti-cancer therapy.
 - d. Follow-up period: unless patient had discontinued study treatments for radiologic disease progression or withdrawal of consent, obtain tumour assessments within 8 weeks after the last previous tumour assessment and then every 8 weeks (\pm 10 calendar days) until documentation of radiologic disease progression, regardless of initiation of a new anticancer therapy
7. Vital signs, including body temperature, pulse rate, respiratory rate, blood pressure, oxygen saturation by pulse oximetry
8. Study procedures prior to the first study treatments administration: to be done at C1D1 prior to study treatments administration only if baseline procedures have been done more than 7 days prior to C1D1
9. Study procedures obtained within 48 hours prior to study treatments administration (trifluridine/tipiracil intake in Arm B of Randomised part on CXD1)
10. To be performed only for futuximab/modotuximab participants (Arm A)
11. Pregnancy testing
 - a. Pregnancy testing at screening period: with serum β HCG test only (Within 7 days prior to first administration of first IMP)
 - b. Pregnancy tests should be performed at the beginning of each cycle during the treatment period, upon treatment discontinuation, at the first follow-up visit, and additionally if clinically indicated, for all relevant patients. More frequent pregnancy tests should be performed if required by local law or as clinically indicated.
12. ECG assessment: To include standard 12-lead ECG with measurement of PR interval, QRS duration, time from the beginning of the QRS complex, representing ventricular depolarization, to the end of the T wave, resulting from ventricular repolarization (QT) interval, and QTc interval [ms], as well as heart rate [beats per minute (BPM)]
To be evaluated locally: ECGs should be performed using the calibrated instrument at each study centre and should be conducted after the participant has been supine (or semi recumbent) for $>$ 10 minutes. Participants with a QTc interval $>$ 480 ms at baseline are excluded. Participants with a QTc interval $>$ 480 ms during the treatment period should not be treated; dosing to be delayed.
In the event of significant electrolyte abnormalities, the evaluation frequency should be increased to include additional evaluations between the scheduled assessments, as clinically indicated. For futuximab/modotuximab participant, an ECG should be performed in the event of \geq Grade 3 hypomagnesemia
13. QoL Assessment: QoL Assessment will be done at baseline, after the end of cycle 1 (C2D1), then from cycle 3 (C3D1) every 2 cycles during the treatment period, at the withdrawal visit and every 8 weeks (2 months) during the follow-up period, until death or until end of the study is reached (whichever occur first). Evaluation by participant reporting questionnaires including: EORTC QLQ-C30 (v3) and EQ-5D-5L
14. Blood haematology: In the event of haematologic toxicity, the evaluation frequency should be increased to include additional evaluations between the scheduled assessments, as clinically indicated
15. Urinary biochemistry: Collect urine samples
16. PK/ADA assessment
 - *i.e. 5-60 minutes before infusion of futuximab/modotuximab
 - **i.e. within 10 minutes before to the end of infusion of futuximab/modotuximab
 - ***The frequency of futuximab/modotuximab immunogenicity assessments will be reduced to every 2 months after the first 6 months in the first year and every 4 months after the first year.
17. Genomic analysis from peripheral whole blood sample for defining patient eligibility and stratification will be based on assessment of ctDNA in plasma with an oncogene panel. After isolation of the plasma, the samples will be submitted for mutation analysis prior to randomisation. The genomic analysis includes a series of genes frequently mutated in cancer, but will be focused on the following genes:
 - BRAF CCI [REDACTED]
 - KRAS & NRAS CCI [REDACTED]
 - EGFR-ECD CCI [REDACTED]
18. Exploratory biomarkers from peripheral whole blood sample collected pre-dose at C1D1, C2D1, C3D1, then every 2 cycles along with tumour assessment and at withdrawal, for ctDNA monitoring

Futuximab/modotuximab

Amended clinical study protocol no. CL3-95026-001 – Final version

ctDNA = circulating tumour DNA; *D* = day; *ECG* = electrocardiogram; *ECOG* = Eastern Cooperative Oncology Group; *INCL* = inclusion; *EoI* = end of infusion; *IV* = intravenous; *SCR* = screening.

For further practical details, methods of measurement are provided in [Sections 7](#) and [8](#).

The approximate total volume of blood collected per participant will be 45 mL for the screening period, < 130 mL **per cycle** for the Cycle 1 and Cycle 2, < 80 mL **per cycle** for the further cycles and <55 mL for WV ([Appendix 12](#)). For men and post-menopausal women, the total volume of blood collected will be slightly lower (since pregnancy tests do not apply).

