	SCR	INCL	Cycle 1				Cycle 2				Cycles 3 and after				WV within 4 weeks after treatment withdrawal and before new anticancer treatment	Follow-up period Every 8 weeks, until death or end of study	Protocol section
			D1	D8 ± 2 days	D15 ± 2 days	D22 ± 2 days	D1	D8 ± 2 days	D15 ± 2 days	D22 ± 2 days	D1	D8 ± 2 days	D15 ± 2 days	D22 ± 2 days			
PHARMACOKINETICS																	
Blood sample for futuximab/modotuximab ¹²			X pre-dose*; EoI**; 1-2h after EoI	X pre- dose*; EoI**; 0.5- 1h after EoI	X		9.2										
Blood sample for trifluridine/tipiracil ¹²			X pre-dose*; EoI**; 1-2h after EoI	X pre- dose*; EoI**; 0.5- 1h after EoI			X pre- dose*; EoI**; 0.5- 1h after EoI	X pre- dose*; EoI**; 0.5- 1h after EoI						X			
Anti-futuximab/ modotuximab antibodies ¹²			X pre-dose*		X pre- dose*		X pre- dose*		X pre- dose*		X pre- dose* ***			X		9.5	
GENOMIC ANALYSIS																	9.1.1.3
Blood sample for ctDNA ¹³	X																
BIOMARKERS																	9.4
Blood exploratory biomarkers ¹⁴			X pre-dose				X pre-dose				X pre-dose			X			

Futuximab/modotuximabAmended clinical study protocol no. CL3-95026-001 – Final version

1. Sign Informed Consent Form (ICF): written informed consent must be obtained during the screening visit, prior to the performance of any study procedure
2. Futuximab/modotuximab administration: futuximab/modotuximab will be administered at a dose 9 mg/kg on Cycle 1 Day 1 (C1D1) (loading dose) and then at a 6 mg/kg weekly (\pm 2 days) beginning on C1D8 (maintenance doses), by IV infusion
3. Trifluridine/tipiracil administration: Trifluridine/tipiracil will be administered at a dose 35 mg/m²/dose, orally twice a day, within 1 hour after completion of morning and evening meals, 5 days on/2 days off, over 2 weeks, followed by a 14-day rest (or in accordance with the local SmPC (Summary of Product Characteristics) of trifluridine/tipiracil)

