6.1.3.2. Schedule

- Trifluridine/tipiracil should be administered before futuximab/modotuximab administration.
- Trifluridine/tipiracil should only be given on Days 1 through 5 and Days 8 through 12 of each cycle. If doses are missed or held on those days, the participant should not make up for missed doses. Extension of study treatment into Days 6 to 7 or into the rest period (Days 13 through 28) is not permitted.
- Trifluridine/tipiracil should be taken with a glass of water within 1 hour after completion of morning and evening meals (or in accordance with the local SmPC of trifluridine/tipiracil).
- Any missed doses reported by the participant should be recorded in the e-CRF.
- Trifluridine/tipiracil dosage is calculated according to BSA (Body Surface Area). Table (6.1.3.2) 1 shows the number of tablets that are needed per calculated BSA for a dose of 35 mg/m². Table (6.1.3.2) 2 shows the number of tablets that are needed per calculated BSA for a reduced dose (30 mg/m², 25 mg/m² and 20 mg/m²). The BSA will be calculated by the site (in Safety Lead-In part) or IWRS (in Randomised part) using the following DuBois formula³⁰ all BSA calculations are rounded to 2 decimal places): BSA (m²) = ([Body Weight (kg)]^{0.425} x [Height (cm)]^{0.725}) x 0.007184.
- If at the beginning of the new treatment cycle, a participant's body weight decreases by $\geq 10\%$ from baseline, the site (in Safety Lead-In part) or IWRS (in Randomised part), will recalculate the participant's BSA and adjust trifluridine/tipiracil dosage.
- In case of change of dose level in Randomised part, the IWRS will provide the study site with the adjusted trifluridine/tipiracil dosage.
- No increase in trifluridine/tipiracil dose due to increase in BSA is permitted.

Table (6.1.3.2) 1 - Number of tablets of trifluridine/tipiracil per dose (standard dose) according to body surface area

Trifluridine/tipiracil Dose (2 x daily)	BSA (m ²)	Dosage in mg (2x daily)	Total daily dose (mg)	Tablets per dose (2x daily)	
				15 mg/6.14 mg	20 mg/8.19 mg
35 mg/m ²	< 1.07	35	70	1	1
	1.07 - 1.22	40	80	0	2
	1.23 - 1.37	45	90	3	0
	1.38 - 1.52	50	100	2	1
	1.53 - 1.68	55	110	1	2
	1.69 - 1.83	60	120	0	3
	1.84 - 1.98	65	130	3	1
	1.99 - 2.14	70	140	2	2
	2.15 - 2.29	75	150	1	3
	≥ 2.30	80	160	0	4

BSA = body surface area (calculate to 2 decimal places)

Table (6.1.3.2) 2 - Number of tablets of trifluridine/tipiracil per dose (reduced dose) according to body surface area

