9.2. Measurement of drug concentration

9.2.1. Sample Collection Timepoints

Blood samples for the evaluation of PK are to be collected at the timepoints listed in [Table \(9.2.1\) 1](#) and [Table \(9.2.1\) 2](#). The accurate sampling dates and times must be recorded in the e-CRF.

Table (9.2.1) 1 - Sample collection timepoints for futuximab/modotuximab and trifluridine/tipiracil (Pharmacokinetics during the Safety Lead-In and Arm A of Randomised part)

	Futuximab and modotuximab assessment	Trifluridine and tipiracil assessment
C1D1	Pre-dose*	Pre-dose*
	End of infusion**	End of infusion**
	1-2 hours after end of infusion	1-2 hours after end of infusion
C1D8	Pre-dose*	Pre-dose*
	End of infusion**	End of infusion**
	30 min-1 hour after end of infusion	30 min-1 hour after end of infusion
C1D15	Pre-dose*	Pre-dose*
	End of infusion**	End of infusion**
	30 min-1 hour after end of infusion	30 min-1 hour after end of infusion
C1D22	Pre-dose*	Pre-dose*
	End of infusion**	End of infusion**
	30 min-1 hour after end of infusion	30 min-1 hour after end of infusion
C2D1	Pre-dose*	Pre-dose*
	End of infusion**	End of infusion**
	30 min-1 hour after end of infusion	30 min-1 hour after end of infusion
C2D8	Pre-dose*	Pre-dose*
	End of infusion**	End of infusion**
	30 min-1 hour after end of infusion	30 min-1 hour after end of infusion
C2D15	Pre-dose*	Pre-dose*
	End of infusion**	End of infusion**
	30 min-1 hour after end of infusion	30 min-1 hour after end of infusion
C2D22	Pre-dose*	Pre-dose*
	End of infusion**	End of infusion**
	30 min-1 hour after end of infusion	30 min-1 hour after end of infusion
CXD1	Pre-dose*	
WV	During the visit	During the visit

*i.e. 5-60 minutes before infusion of futuximab/modotuximab

**i.e. within 10 minutes before to the end of infusion of futuximab/modotuximab

Table (9.2.1) 2 - Sample collection timepoints for trifluridine/tipiracil (Pharmacokinetics in Arm B of Randomised part)

	Trifluridine and tipiracil assessment
C1D1	At the beginning of the visit
	At the end of the visit
C1D15	During the visit
C2D1	During the visit
C2D15	During the visit
WV	During the visit

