Appendix 12: Maximum Total Blood Collection Volumes

	Treatment period												
	Volume/ sample	Screening /Inclusion		Cycle 1		Cycle 2		Cycle 3		Further from Cycle 4		Withdrawal Visit	Total (ml)
		#	Volume mL	#	Volume mL	#	Volume mL	#	Volume mL	#	Volume mL	#	Volume mL
Genomic analysis													
Blood sample for ctDNA	20	1	20	0	0	0	0	0	0	0	0	0	20
Biomarker													
Blood exploratory biomarkers*	20	0	0	1	20	1	20	1	20	0	0	1	20
Safety assessment													
Haematology	5	1	5	2	10	2	10	2	10	2	10	1	5
Biochemistry	10	1	10	2	20	2	20	2	20	2	20	1	10
Additional Biochemistry for Mg, Ca, K	5	0	0	2	10	2	10	2	10	2	10	0	0
Coagulation	5	1	5	1	5	1	5	1	5	1	5	1	5
β hCG test	5	1	5	1	5	1	5	1	5	1	5	1	5
Pharmacokinetics													
PK evaluation for futuximab/modotuximab	2.5	0	0	12	30	12	30	1	2.5	1	2.5	1	2.5
PK evaluation for T/T	4	0	0	6	24	6	24	0	0	0	0	1	4
ADA													
ADA (2.5 mL) for futuximab/modotuximab**	2.5	0	0	2	5	2	5	1	2.5	1	2.5	1	2.5
TOTAL volume (mL)			45		129		129		75		55		54
													487

Abbreviations (in alphabetical order): #, number of samples; ADA, anti-drug antibody; Ca, calcium; K, potassium; Mg, magnesium; mL, millilitre; PK, pharmacokinetic; T/T, trifluridine/tipiracil

* C1D1, C2D1, C3D1 then every 2 cycles

** The frequency of ADA assessments will be reduced to every 2 months after the first 6 months in the first year and every 4 months after the first year.

If sites can perform haematology, serum chemistry, and coagulation studies with smaller volumes of blood per sample, they are encouraged to do so. Required PK, ADA, and PD/biomarker volumes are fixed and should not be reduced.

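### For the Safety Lead-In and Arm A, Table (9.2.1) 1 lists twice as many trifluridine/tipiracil PK samples in Cycles 1 and 2 as Appendix 12 counts; following it takes up to 153 mL of blood per cycle against a stated limit of under 130 mL

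*Protocol*

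**What the plan says.** Section 4.1.2 begins its volume statement "The approximate total volume of blood collected per participant will be 45 mL for the screening period, < 130 mL"; the limits for the treatment cycles are "< 130 mL per cycle for the Cycle 1 and Cycle 2, < 80 mL per cycle for the further cycles". It points to Appendix 12, which is headed as a table of maximum volumes. The last row there reads "TOTAL volume (mL) 45 129 129 75 55 54" (screening, Cycle 1, Cycle 2, Cycle 3, later cycles, withdrawal visit). Its trifluridine/tipiracil row reads "PK evaluation for T/T 4 0 0 6 24 6 24 0 0 0 0 1 4": 4 mL per sample, 6 samples (24 mL) in each of Cycles 1 and 2, and one at withdrawal.

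The investigation schedules, Tables (4.1.2) 1 and 2, fill the trifluridine/tipiracil PK row (Arm A in Table 2) at four visits in Cycles 1 and 2, namely C1D1, C1D8, C2D1 and C2D8. Each has a pre-dose, an end-of-infusion and a post-infusion sample. There is one more at withdrawal. For PK, both tables refer to Section 9.2.

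Section 9.2.1 then gives "Sample collection timepoints for futuximab/modotuximab and trifluridine/tipiracil (Pharmacokinetics during the Safety Lead-In and Arm A of Randomised part"). Its trifluridine/tipiracil column has three samples at each of eight visits: Days 1, 8, 15 and 22 of Cycles 1 and 2. Section 9.2.2 confirms 4 mL per sample.

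On dosing, Section 6.1.3.2 limits trifluridine/tipiracil to Days 1 to 5 and 8 to 12 and adds: "Extension of study treatment into Days 6 to 7 or into the rest period (Days 13 through 28) is not permitted".

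**The concern.** A site that starts from the schedule table is sent to Section 9.2 for PK and finds a different sample list there. The stated volume rests on the shorter list, so a site that follows Section 9.2.1 to the letter can exceed a figure the protocol presents as a maximum. Appendix 12 also says that PK volumes are fixed and should not be reduced, so the excess cannot be absorbed by smaller PK tubes. Two sites, each working from a valid part of the protocol, would return different sets of trifluridine/tipiracil concentrations, and each could record the other's practice as a deviation.

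**Working it through.** **Inputs** (Appendix 12, Cycle 1; Cycle 2 is identical), samples × mL:

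- exploratory biomarkers 1 × 20 = 20
- haematology 2 × 5 = 10
- biochemistry 2 × 10 = 20
- additional Mg, Ca, K 2 × 5 = 10
- coagulation 1 × 5 = 5
- β-hCG 1 × 5 = 5
- futuximab/modotuximab PK 12 × 2.5 = 30
- ADA 2 × 2.5 = 5
- trifluridine/tipiracil PK 6 × 4 = 24

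**Step 1, the plan's own figure.** Without trifluridine/tipiracil PK: 20 + 10 + 20 + 10 + 5 + 5 + 30 + 5 = 105 mL. Adding 24 gives 129 mL, as stated. Across periods, 45 + 129 + 129 + 75 + 55 + 54 = 487 mL, also as stated. The appendix is internally correct.

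**Step 2, sample counts per cycle** (the withdrawal sample is common to all sources).

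- Schedule tables: 2 visits × 3 = 6.
- Appendix 12: 6. It gives counts, not visits, but 6 at three per visit is two visits.
- Table (9.2.1) 1: 4 visits × 3 = 12.

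**Step 3, volume if Table (9.2.1) 1 is followed.** 12 × 4 = 48 mL, so 105 + 48 = 153 mL per cycle. That is 153 − 130 = 23 mL above the limit, and 23/130 is about 18%. The addition is 6 samples and 24 mL per cycle, or 12 samples and 48 mL over two cycles. The total becomes 487 + 48 = 535 mL.

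**Step 4, participants below the maximum.**

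- No blood pregnancy test: 153 − 5 = 148 mL.
- Cycle 1 only: C1D1 safety bloods are repeated only if baseline was more than 7 days earlier. Leaving out haematology 5, biochemistry 10 and coagulation 5 gives 153 − 20 = 133 mL, or 128 mL with no pregnancy test either.
- Cycle 2: those bloods are unconditional, so at Appendix 12 volumes the range is 148 to 153 mL and every participant exceeds 130 mL.

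**Step 5, where the extra samples fall.** They are on Days 15 and 22. Even with the 2-day visit window the earliest is Day 13, so all 12 lie in the trifluridine/tipiracil rest period. Futuximab/modotuximab is infused on both days, and its own PK is drawn at the same three time points.

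**The case against.** The strongest case is that this is a small cross-table slip with little consequence. Section 4.1.2 calls its volumes approximate. 153 mL is a ceiling. Appendix 12 encourages smaller tubes for haematology, chemistry and coagulation. The extra 4 mL tubes are taken at draws that already happen for the antibody. The SAP (Section 1) records that the Randomised part was cancelled, and its Section 1.1 limits the analysis to the primary analysis and best overall response. All of this is true and limits the impact to Safety Lead-In conduct and any reuse of the protocol. It does not remove the contradiction, nor the fact that the stated limit holds for only one of the two sample lists.

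A second objection is to the evidence. In the text copy of the protocol, rows near the one at issue in the schedule tables are misaligned, so the cell positions should be checked against the original. The finding does not depend on them: Appendix 12 independently gives 6 samples per cycle. Table (9.2.1) 1 keeps an empty trifluridine/tipiracil cell at CXD1, which speaks against entries having been duplicated when the text was read.

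A reader might infer more than the documents support:

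- *That no drug is given when the extra samples are taken.* Only trifluridine/tipiracil is paused; the antibody mixture is infused on Days 15 and 22.
- *That the samples add nothing to PK and could be deleted without loss.* Table (9.2.1) 2 samples trifluridine/tipiracil in Arm B at C1D15 and C2D15, also in the rest period. PK parameters are to come from population modelling, and nothing in the protocol calls late concentrations uninformative.
- *That the volume matters because Grade 3 anaemia is a DLT.* No document links an extra 24 mL per cycle to anaemia.

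**Conclusion.** The contradiction stands. For the Safety Lead-In and Arm A, the limit of under 130 mL per cycle is met with 6 trifluridine/tipiracil samples per cycle (129 mL) and fails with the 12 in Table (9.2.1) 1 (maximum 153 mL). In Cycle 2 the excess applies to every participant at the tabulated volumes; in Cycle 1 a participant with recent baseline bloods and no pregnancy test stays under, at 128 mL. The figures assume Appendix 12 tube sizes and that all listed samples are taken. Arm B has its own sampling table and is not affected. Whether the patient information repeats the lower volume cannot be seen from the protocol and SAP.

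**What to change.** Reconcile Section 9.2.1 with Section 4.1.2 and Appendix 12 in one of two ways; the sponsor decides which sample list was intended.

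1. Remove the trifluridine/tipiracil entries at Days 15 and 22 of Cycles 1 and 2 from Table (9.2.1) 1, after confirming that the Day 15 samples are not wanted as the counterpart of Arm B's in Table (9.2.1) 2. This edits one table and leaves the stated volumes as they are. The cost is 12 fewer trifluridine/tipiracil samples per participant than Section 9.2.1 now asks for.
2. Keep the entries. Then add them to Tables (4.1.2) 1 and 2, change the trifluridine/tipiracil row of Appendix 12 to 12 samples (48 mL) in each of Cycles 1 and 2, and restate the maximum as 153 mL per cycle and 535 mL in total, in Section 4.1.2 and Appendix 12. Correct the patient information too if it quotes the lower volume. The cost is a wider text change and 48 mL more blood per participant than now stated.

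For samples already collected in the Safety Lead-In, the report should say which list sites followed.

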4.1.3. Safety Lead-In Part

The Safety Lead-In part is an open-label, single-arm and non-randomised study phase in approximately 25 participants. A minimum of 3 Japanese participants will be enrolled. During this part, the safety and tolerability of futuximab/modotuximab in combination with trifluridine/tipiracil will be evaluated prior to the start of the Randomised part. Efficacy parameters, futuximab/modotuximab and trifluridine/tipiracil PK and futuximab/modotuximab immunogenicity will also be evaluated as secondary endpoints.

The Study plan of Safety Lead-In part is depicted in [Figure \(4.1.1\) 2](#). The schedule of study assessments is provided in [Table \(4.1.2\) 1](#).

4.1.3.1. Dose administration schedule

The therapeutic regimen for the Safety Lead-In part [Figure \(4.1.1\) 2](#) is as follows:

- Trifluridine/tipiracil (35 mg/m² BID) 5 days on/2 days off over 2 weeks followed by 14 days off, before futuximab/modotuximab administration.
- Futuximab/modotuximab (9 mg/kg) loading dose on C1D1 followed by (6 mg/kg) weekly maintenance doses.

4.1.3.2. DLT definition

For each participant, DLT assessment will be performed during Safety Lead in part. Assessments include all toxicities observed during the initial 28-day treatment period (Cycle 1). A DLT is defined as:

- A clinically significant adverse event (AE) graded according to the National Cancer Institute Common Terminology Criteria for Adverse Events (NCI-CTCAE) version 5.0 observed during the initial 28-day treatment period following the first IMP administration.
- Assessed as unrelated to underlying disease, disease progression, intercurrent illness, or concomitant medications.
- At least possibly related to the IMPs (Futuximab/modotuximab or Trifluridine/tipiracil or both) by the investigator and meeting any of the criteria included in [Table \(4.1.3.2\) 1](#).

Table (4.1.3.2) 1 - Dose-limiting toxicity criteria

Toxicity Class	Dose-limiting Toxicity Criteria
Haematological abnormalities	Anaemia \geq Grade 3
	Febrile neutropenia
Gastrointestinal disorders	Uncomplicated Grade 4 neutropenia that lasts \geq 1 week
	Uncomplicated Grade 4 thrombocytopenia (less than $25\ 10^9/L$) that lasts \geq 1 week or any Grade ≥ 3 thrombocytopenia (between 25 and $50\ 10^9/L$) with bleeding episodes or thrombocytopenia requiring platelet transfusion
Skin disorders	Grade 3 diarrhoea for > 2 days despite adequate treatment or with fever and/or dehydration
Infusion-related reactions	Any Grade 3 skin toxicity lasting for more than 2 weeks, or Grade 4 skin toxicity regardless of duration ¹
Hepatic abnormalities	Grade ≥ 3 infusion related reaction
Other adverse events	AST or ALT $\geq 3 \times$ ULN along with a total bilirubin $> 2.0 \times$ ULN and confirmed Hy's law cases according to FDA guidance
	Isolated AST or ALT \geq CTCAE Grade 3
	Any laboratory value Grade ≥ 3 with a duration ≥ 3 days, considered unrelated to underlying disease, disease progression, intercurrent illness or concomitant medications/therapies
	Any Grade 3 or Grade 4 non-haematologic adverse event (except for Grade 3 nausea and/or vomiting controlled by anti-emetic therapy that last less than 72h, or Grade 3 diarrhoea responsive to anti-diarrheal medication)

¹ acne, cellulitis, dermatitis acneiform, dry skin, erysipelas, erythema, folliculitis, hypertrichosis, paronychia, pruritus, rash, rash maculopapular, rash vesicular, skin exfoliation, skin hyperpigmentation and xerosis

Participants who meet any following criteria will not be evaluable for DLT and therefore will be replaced during the Safety Lead-In part of the study.

- Permanently discontinued treatment during DLTs assessment period for reasons other than DLT.
- Did not undergo a DLT assessment at the end of Cycle 1.
- Participants must complete at least the first cycle of treatment with a dose intensity [(administered dose in mg/planned dose in mg) x 100] higher than 75% with a minimum follow-up duration of 28 days. The dose intensity for single-agent trifluridine/tipiracil in Phase 3 studies is approximately 89%; therefore, for the combination a value of 75% is considered appropriate. Participants who require a dose interruption or reduction during the initial 28-day treatment period (Cycle 1) will remain evaluable for tolerability decisions if the reason for the reduction and/or interruption is a DLT. Participants will be replaced if they have received fewer than 75% dose intensity of trifluridine/tipiracil or futuximab/modotuximab for any reason other than an AE or abnormal laboratory value that is not related to their disease, disease progression, intercurrent illness or concomitant medications/therapies.

